Before the video assessment, potential participating parents and children will be provided with both written and oral information about the study. If willing to participate, we will collect written informed consents from the parents and oral informed consents from the children. Oral consents from children will be collected during the video conferencing call. During the video call, parents will answer questions about their own and their children's mental health. A licensed psychologist will administer two semi-structured diagnostic interviews (M.I.N.I. and ADIS) to collect information about anxiety disorders as well as other psychiatric disorders. After the diagnostic video interview, the research team will decide if the parents meet inclusion criteria or not.

Parents who are included will receive an email with personal login information to a battery of questionnaires (baseline assessment). The parents are then randomly assigned to either (1) the intervention group, *Confident Parents - Brave Children* (CPBT) or (2) the active comparator group (reading a self-help book).

The CPBT will contain 6 group sessions during a period of 10 weeks. Individual booster sessions with all participants will be scheduled one month after the last group session. All group leaders will be licensed psychologists.

At the end of the intervention phase (after the booster session), the participants will receive an email with personal login information to complete a battery of questionnaires (post assessment).

Follow-up, semi-structured diagnostic interviews are conducted 12- and 36-month post-treatment. The participants will also complete a battery of questionnaires at 12- and 36-month follow-ups. An overview of the study is provided in figure 1 below.

Measures

Primary outcome measure

The primary outcome will be change in severity of childhood anxiety disorder, as rated by clinician at 12- and 36-months follow-up. Clinical Severity Ratings (CSR) range from 0 to 8, where a value of 4 and higher indicate that the child meets criteria for an anxiety disorder. The CSR is extracted from the Anxiety Disorders Interview Schedule - Schedule for Children (ADIS-C). The CSR is rated by clinician based on interviewing with primary caregiver.

Secondary outcome measures - parent reported

EQ5D

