We hypothesize that helping parents gain more knowledge of childhood anxiety and use more positive parenting skills would produce warmer parenting and more acceptance of the child. We hypothesize that helping parents understand the consequences of overprotective behaviour and find opportunities to help their child in challenging/approaching behaviour would increase the autonomy of their child. We believe that helping parents challenge their own fears and remember to reward their child for approaching behaviours would increase modelling and reinforcement of approaching behaviours. Subsequently, we hypothesize that parental warmth and acceptance, increased autonomy of the child, and modelling and reinforcement of approaching behaviour would, in the long term, decrease the risk of developing an anxiety disorder. CPBT comprise six 120-minute group sessions and one individual booster sessions. All sessions will be carried out using Zoom.

Participants in the active control group will receive a parenting book containing research-based strategies for handling children's anxiety [12]. They will be instructed to read the book within the 10 weeks from baseline to post assessments but will receive no other guidelines. They will not receive any help from the research team while working with the book.

Efficacy: Data-Analysis

The efficacy of the CPBT will be evaluated in a series of regression analyses. The primary outcome measure (child CSR) will be evaluated in a generalized linear mixed model (GLMM). The measures EEAC, OP, FASA-PR and MPAQ will be evaluated separately as dependent variables using the linear mixed model (LMM).

Cost-Effectiveness

Two types of analyses (cost-utility analysis and cost consequence analysis) will be performed. The cost-utility analysis will be expressed as an incremental cost effectiveness ratio given as the difference in costs divided by the difference in quality-adjusted life years (QALYs) for parents and children between the two conditions (i.e. the cost for one additional life year with full health gained). In the cost-consequence analysis, incremental costs and outcomes per parent and /child between the conditions will be presented for each cost and outcome item. Costs in both trial arms will be estimated from a limited societal perspective. Costs will be calculated for each participant based on resource items and associated relevant unit costs. Costs to deliver the intervention will be estimated based on practitioners' time to

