deliver the intervention, costs for materials, etc., using a micro-costing framework. The use of other societal resources by children and their parents will be collected at baseline and at 12 months follow-up. This comprises information on the use of resources related to healthcare and productivity losses due to absence from school for children, and productivity losses due to absence from work for parents, which will be collected using an adapted version of the questionnaire on healthcare consumption and productivity losses (TiC-P) [29]. The TiC-P is a feasible and reliable instrument for collecting data on medical consumption and productivity losses in individuals with mild to moderate mental health problems. Total costs will be aggregated by trial arm.

As the economic data are likely to be missing at random, multiple imputation methods will be used in the base case analysis. Total QALY gains for parents and children over the trial period will be estimated using the area under the curve method. Cost data and QALYs will be analyzed using generalized linear models (GLM) to account for non-normal distribution. The GLM approaches allow the consideration of other distributions and functional forms to fit the costs data. Data will be analyzed while controlling for covariates and adjusting for baseline values.

Safety procedures and adverse events

If a child meets criteria for an anxiety disorder when the first diagnostic interview is carried out, the family is excluded and referred to health care. If the parent suffers from substance or alcohol abuse or severe psychiatric illness, or in case of domestic violence, the family will be excluded and referred to health care or social services.

Parents and children are free to seek care for mental health problems while participating in the study. Only licensed psychologists will carry out the diagnostic assessments and be responsible for leading the parenting groups. To prevent any possible concern about data safety among the participants, there will be information on how data is securely handled. All participant data will be handled confidentially. Data will be imported to a coded data file and the investigators will perform all analysis.

In case of an adverse event, the members of the research team will inform the study coordinator ([name]) who will be responsible for deciding what actions are appropriate to take. Any adverse events will be described in the planned publication.

Project schedule

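### Adverse events have no scheduled enquiry, and team contact during the intervention phase is about 7 against 0, so events other than symptom worsening are likely to be recorded unequally by arm

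*Protocol*

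**What the plan says.** The Protocol, under Safety procedures and adverse events, describes how an event is passed on: "In case of an adverse event, the members of the research team will inform the study coordinator". The coordinator then decides what to do. On reporting it says: "Any adverse events will be described in the planned publication". It gives no definition, checklist, scheduled question or participant reporting route, and the overview of measures (Table 2) has no adverse-event item.

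The two arms differ in how often the team meets them. Under Intervention, "CPBT comprise six 120-minute group sessions and one individual booster sessions". Of the book parents the same section says: "They will not receive any help from the research team while working with the book".

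After the intervention the Procedure treats the arms alike. Both get the emailed post questionnaires. Then, "Follow-up, semi-structured diagnostic interviews are conducted 12- and 36-month post-treatment", and "The participants will also complete a battery of questionnaires at 12- and 36-month follow-ups".

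**The concern.** If events reach the record mainly because a team member hears of them, the number recorded depends on how often the team meets the family. In the intervention phase that contact belongs almost wholly to the CPBC arm. An event in a CPBC family can come up in any of seven live sessions led by a psychologist. The same event in a book family has no scheduled live occasion to come up until the interview 12 months after treatment, when it may be forgotten or thought irrelevant.

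What is at stake is the account of harms, not the primary outcome or the power. A reader of a two-arm trial report will look at events by arm. With unequal collection, the programme under test may look more harmful than the book although the true risks are equal, and the arm without support is the one least observed.

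**Working it through.** The plan gives no adverse-event rate or detection rate, so there is no figure of its own to reproduce on this point. What can be checked is the number of scheduled live contacts after randomisation and what that number implies.

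**Contacts**

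| Period | CPBC | Book | Source (Protocol) |
|---|---|---|---|
| Intervention phase | 6 + 1 = 7 | 0 | Intervention |
| Up to and including the 12-month interview | 7 + 1 = 8 | 0 + 1 = 1 | Procedure |
| Up to and including the 36-month interview | 8 + 1 = 9 | 1 + 1 = 2 | Procedure |

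One sentence in the Procedure bears on the zero: "Individual booster sessions with all participants will be scheduled one month after the last group session". It stands in the paragraph on the programme and is timed from the last group session, so I read it as CPBC only. Read literally, it would make the intervention-phase count 7 against 1.

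**Illustration**

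Assumptions, none of them from the documents:
- the true risk is the same in both arms;
- each contact has the same chance d of bringing an event to light, independently of the others;
- the event is present early enough to come up at every contact.

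The chance that an event is recorded after k contacts is 1 − (1 − d)^k. The true risk cancels from the ratio between arms.

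| d | 9 contacts | 2 contacts | Ratio 9 v 2 | 8 contacts | 1 contact | Ratio 8 v 1 |
|---|---|---|---|---|---|---|
| 0.1 | 0.613 | 0.190 | 3.2 | 0.570 | 0.100 | 5.7 |
| 0.3 | 0.960 | 0.510 | 1.9 | 0.942 | 0.300 | 3.1 |
| 0.5 | 0.998 | 0.750 | 1.3 | 0.996 | 0.500 | 2.0 |

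The 8 v 1 column matters because the Project schedule puts publication in summer to fall 2023. A 36-month interview of the first cohort, recruited in spring 2021, cannot fall before 2024.

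**In counts.** The sample size section gives 194 / 0.9 = 215.6, so 216 children. With equal allocation assumed, that is 108 per arm. At an assumed true risk of 10% there are 10.8 events per arm. With both interviews, recorded events are 6.6 against 2.1 (d = 0.1), 10.4 against 5.5 (d = 0.3) and 10.8 against 8.1 (d = 0.5).

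**If the booster covers book parents too.** The counts become 9 v 3 and 8 v 2. For d = 0.1, 0.3 and 0.5:
- 9 v 3: 0.613/0.271 = 2.3, 0.960/0.657 = 1.5, 0.998/0.875 = 1.1.
- 8 v 2: 0.570/0.190 = 3.0, 0.942/0.510 = 1.8, 0.996/0.750 = 1.3.

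The imbalance shrinks but keeps its direction.

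**The case against.** The strongest reply is that the harm most relevant to a parenting programme or a parenting book is worsening of symptoms, and the plan measures that in the same way in both arms. SCARED-R, PHQ-9 and PROMIS Anxiety are collected at post, 12 and 36 months, and the clinician's CSR for the child at 12 and 36 months. The TiC-P adds healthcare use and absence from school and work at 12 months. This stands. A reader might infer that deterioration in book families goes unseen, and the documents do not support that. What remains is narrower: events these instruments do not cover, and late recognition. Nothing in the text links the scores to adverse-event reporting.

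Three other stronger readings also fail:

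- **That the team never meets book parents.** This holds for the intervention phase only. Both arms have the 12- and 36-month interviews.
- **That an event can enter only if a team member notices it.** The safety section is a rule for passing on a known event. It does not stop a parent from telling the team. The point rests on the absence of any planned question, not on a prohibition.
- **That a formal comparison of adverse events is planned.** The Protocol promises only a description. The worry is how that description will be read if set out by arm.

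It is also fair to say that the detection chances are assumed, and that an event arising after the last session has the same scheduled contacts in both arms. The ratios therefore apply to events that begin early. With a high chance of detection and both interviews counted, the ratio comes down to 1.3.

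**Conclusion.** The point holds in limited form. The plan has no scheduled adverse-event enquiry, and scheduled live contact in the intervention phase is 7 against 0 (7 against 1 at most), about 9 against 2 over the whole trial. Events other than symptom worsening are more likely to be missed or found late in the book arm, and a description by arm may be unfavourable to CPBC with no true difference.

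The contact counts follow from the text. The size of the distortion does not, since it depends on equal true risk, early events and the assumed chance of detection per contact. The direction is the same in every case examined. Efficacy results are not affected. How adverse events are collected belongs in a protocol, so this is not a matter left to an analysis plan.

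**What to change.** Add the same brief adverse-event questions, about the parent and about the child, to the post, 12- and 36-month assessments in both arms. Put them in the online battery at all three time points and in the follow-up interviews at 12 and 36 months. Use the same wording and recall period in each arm, and state what counts as an adverse event so that answers are classified alike.

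In the publication, describe events by arm from these common sources, keeping those found in the follow-up interviews, which both arms receive. List events noticed only in CPBC sessions separately as spontaneous reports. State also whether the booster session includes book parents.

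The cost is a few items in assessments already planned, and more minor events to log. Questions at these time points make collection even between arms, but they do not by themselves make detection prompt.
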